9.7.1 Genetics

Whole blood samples for DNA genotyping will be collected according to the flowchart in Section 2 for future analysis and long-term storage from patients who have consented to participate in this part of the trial. Participation in the genetic research is optional. Patients who do not wish to participate in the genetic research may still participate in the trial.

In the event of sample handling failure, a replacement genetic blood sample may be requested from the patient.

Genetic samples will not be evaluated by the investigator.

Patients who had a sample taken at visit 1 before the treatment pause should not have that sample re-taken upon trial restart.

Please refer to Appendix 9 for further information regarding the genetic research. Details on processes for collection, shipment and destruction of these samples can be found in the laboratory manual.

9.7.2 **Biomarkers**

Serum and plasma samples will be collected according to the flowchart in Section 2 for future exploratory laboratory analysis and long-term storage from patients where additional consent has been obtained. Patients who do not wish to participate in this research may still participate in the trial.

Biomarker samples will not be evaluated by the investigator.

Protocol Trial ID: NN7415-4307	CONFIDENTIAL	Date: Version: Status: Page:	25 March 2021 5.0 Final 82 of 138	Novo Nordisk
-----------------------------------	--------------	---------------------------------------	--	--------------

Patients who had a sample taken at visit 1 before the treatment pause should not have that sample re-taken upon trial restart.

Please refer to Appendix 9 for further information regarding the biomarker research and details on processes for collection, shipment and destruction of these samples can be found in the laboratory manual.

Status:

Page:

83 of 138

9.8 Health economics

A set of eDiary screens assembled in a monthly diary will be made available to the patient every 30 days. The screens are designed to collect:

- Number of school or workdays missed
- Number of days where a patient used an aid to move around
- How many days in-home professional nursing was needed.

The monthly diary will be completed by the patient in the eDiary.

9.9 Surgery

Minor surgical procedures are allowed during the trial (for surgery definitions see Table 14). Planned major surgery is not allowed.

Haemophilia A and haemophilia B patients undergoing minor surgical procedures should be managed in accordance with local standard of care. Coagulation factor replacement therapy using either regular or extended half-life products are allowed and should be used in accordance with local label.

Local/topical use of antifibrinolytics e.g. tranexamic acid is allowed. Use of single systemic doses is allowed after careful benefit-risk evaluation.

During the perioperative period patients should continue daily concizumab prophylaxis.

Table 14 **Surgery definitions**

Category	Definition	Examples
		A body cavity is entered
	Any invasive operative procedure that	A mesenchyme barrier (e.g. pleura,
Major surgony	requires ≥3 doses of replacement therapy	peritoneum or dura mater) is crossed
Major surgery:	and/or where any one or more of the	A fascia plane is opened
	following occur	An organ is removed
		Normal anatomy is operatively altered
		Implanting of central venous access
		devices (ports, central venous catheter,
	A ' ' ' 11	pumps and other central venous access
	Any invasive operative procedure where	devices) in subcutaneous tissue
Minor surgery:	only the skin, the mucous membranes or	Skin biopsies
	superficial connective tissue is	Simple dental procedures
	manipulated	Ear tube/drain insertion
		Circumcision
		Port insertion in paediatric patients

For surgery the following should be recorded in the eCRF:

- Type of Surgery
- Data and stop time and dose of preventive treatment (haemostatic medication).
- Other treatments during surgery (concomitant medication)
- Indication of surgery
- Anatomical Location of surgery
- Date of surgery
- Start and stop time of surgery

Protocol Trial ID: NN7415-4307	CONFIDENTIAL	Date: Version:	25 March 2021 5.0	Novo Nordisk
		Status:	Final	
		Page:	84 of 138	

In the instance of acute major surgery, it is recommended to pause concizumab at the discretion of the investigator.

25 March 2021 Novo Nordisk Date: Version: 5.0 Status:

Page:

Final 85 of 138

Statistical considerations

10.1 Sample size determination

The estimand for the primary objectives will for patients in arms 1 and 2 be addressed based on the Full Analysis Set (FAS; see Section 10.2) using negative binomial regression.

The sample size calculation has been determined based on the estimand for the primary and confirmatory secondary objectives. In the below calculations it is assumed that the treatment duration is 24 weeks for patients in arms 1 and 32 weeks for patients in arm 2. For the comparison of previous PPX to concizumab PPX in arm 4 it is assumed that the treatment duration is 38 weeks (estimated from NN7415-4322 (explorer 6)) on the previous PPX regimen and 24 weeks on the concizumab maintenance dose.

When evaluating the power of the negative binomial analysis with exposure time as offset and treatment as factor, annual bleeding rates of 24 and 18 are assumed for the no-prophylaxis HA patients, and the no-prophylaxis HB patients, respectively. An ABR of 3-5 is expected for concizumab prophylaxis. Assuming further a yearly over-dispersion of 13, the power for concluding superiority of concizumab prophylaxis versus no-prophylaxis for HA patients becomes at least 82% with 21 patients (14 in the concizumab arm and 7 in the comparator arm). The power for concluding superiority of concizumab prophylaxis versus no prophylaxis for HB patients becomes at least 79% with 33 patients (22 in the concizumab arm and 11 in the comparator arm). When evaluating the power of the negative binomial analysis (with exposure time as offset and treatment as factor and incorporating within-subject repeated measurements using an unstructured covariance matrix) with respect to showing non-inferiority of concizumab prophylaxis vs previous prophylaxis in a withinpatient comparison the assumptions are: Concizumab ABR of 3-5, an ABR for previous prophylaxis of 4, a noninferiority margin of 2.0 on the relative scale, a sample size of 30 and a yearly over-dispersion of 13, and a patient's frailty for experiencing bleeds in the first period (on previous PPX) and the second period (on concizumab PPX) is fully correlated. With these assumptions the power will be at least 79% to show non-inferiority for each haemophilia subtype.

ABR assumptions

Based on the available studies and sources, a representative mean ABR on on-demand treatment for the severe haemophilia A patients of 24 bleeds/year and for the haemophilia B patients of 18 bleeds/year is considered appropriate (see Table 15).

Table 15 Annualised bleeding rate recorded in prior Novo Nordisk studies conducted in different haemophilia subpopulations treated on-demand

Regimen	Population	Study	N	ABR
	HA	NN7088-3859a	12	32.35
On demand	HA	NN7008-3568b	19	24
	HB	NN7999-3747°	13	17.6

Note: The ABR is recorded in prior Novo Nordisk studies conducted in different haemophilia subpopulations. *NN7088-3859 CTR extension 1, EOT 14.2.78; bNN7008-3568 CTR, EOT 14.2.65; sNN7999-3747 CTR, EOT 14.2.45

It is the expectation to show an ABR for concizumab prophylaxis of approximately 3-5 bleeds/year.

Date: Version: Status: Page:

25 March 2021 Novo Nordisk 5.0 Final 86 of 138

Over-dispersion assumptions

A yearly over-dispersion of 13 is deemed realistic based on experience from previous trials.

Power

Primary endpoint

Assuming ABRs of 24 and 18 for the no-prophylaxis HA patients, and the no-prophylaxis HB patients, respectively, an ABR between 3 and 7 for the concizumab arm (arm 2) for both HA and HB patients, a yearly over dispersion varying between 11 and 15 and performing 10,000 simulations of each group will produce different scenarios of power in superiority tabulated in Table 16 below.

Table 16 Power for superiority for patients with HA and HB respectively

Power (HAa/HBb)		Yearly over-dispersion	
ABR concizumab	11	13	15
3	94%/95%	91%/92%	88%/89%
4	92%/91%	87%/86%	83%/83%
5	87%/85%	82%/79%	78%/74%
6	83%/77%	75%/70%	70%/64%
7	76%/68%	70%/62%	66%/56%

^aFor HA, power is calculated with 21 patients randomised 2:1 assuming an ABR for the on-demand treatment of 24 ^bFor HB, power is calculated with 33 patients randomised 2:1 assuming an ABR for the on-demand treatment of 18

When evaluating the power of the negative binomial analysis with exposure time as offset and treatment regimen as factor, annual bleeding rates of 24 and 3-5 are assumed for the haemophilia A patient (or 18 and 3-5 for the haemophilia B patient) on no prophylaxis and on concizumab prophylaxis, respectively. Assuming further a yearly over-dispersion of 13, the power for concluding superiority of concizumab prophylaxis becomes at least 82% with 14 patients in the concizumab and 7 patients in the comparator arm for haemophilia A (or at least 79% with 22 patients in the concizumab arm and 11 patients in the comparator arm for haemophilia B; see Table 16).

Confirmatory secondary endpoint

When evaluating the negative binomial analysis (with exposure time as offset, treatment as factor and incorporating within-subject repeated measurements using of an unstructured covariance structure) with respect to showing non-inferiority of concizumab prophylaxis vs previous prophylaxis in a within-patient comparison, the power of showing non-inferiority is at least 79% with a concizumab ABR of 3-5, an ABR for previous prophylaxis of 4, a non-inferiority margin of 2.0 on the relative scale, a sample size of 30, a yearly over-dispersion of 13 and assuming a patient's frailty for experiencing bleeds in the first period (on previous PPX) and the second period (on concizumab PPX) is fully correlated (i.e. a correlation of 1). Other scenarios with different assumptions are displayed in Table 17 below including scenarios where the assumption of a correlation of 1 is lowered to 0.8.

Date: 25 March 2021 Novo Nordisk Version: 5.0 Status: Final

Page:

Final 87 of 138

Table 17 Power to demonstrate non-inferiority separately for patients with HA or HB

			Non-infer	lative scale	
Correlation ^a	ABR on concizumab ABR on previous prophylaxis	1.5	1.8	2.0	
		2	6%	21%	33%
	3	4	95%	99%	>99%
		6	>99%	>99%	>99%
	_	2	~0%	~0%	~0%
1.0	5	4	25%	61%	79%
		6	97%	>99%	>99%
	_	2	~0%	~0%	~0%
	7	4	0%	6%	17%
		6	50%	87%	95%
	_	2	5%	12%	18%
	3	4	66%	83%	89%
		6	96%	99%	>99%
	_	2	~0%	~0%	~0%
0.8	5	4	14%	33%	46%
	6	71%	89%	95%	
	_	2	~0%	~0%	~0%
	7	4	~0%	5%	11%
		6	26%	55%	71%

^a The spearman correlation between a patient's frailty for experiencing bleeds in the first and the second treatment period.

Combined power

Assuming that the confirmatory secondary endpoint is independent of the primary endpoint the combined power becomes at least 82%*79% = 65% for haemophilia A patients and at least 62% for haemophilia B patients.

Expected frequency and pattern of missing data

Since treatment options for haemophilia patients are limited and there is a general tendency to continue with the treatment regimen, the completion rate for this study is expected to be high with less than 15 % withdrawing or discontinuing treatment prematurely. The study will randomise 24 patients with haemophilia A and 36 with haemophilia B to account for potential withdrawals in particular in relation to other endpoints in this trial.

10.2 Definition of analysis sets

The following analysis sets are defined:

• Safety analysis set (SAS): All patients exposed to concizumab PPX or randomised to OnD.

• Full analysis set (FAS): All patients randomised to the new concizumab PPX dosing regimen or OnD after the treatment pause or allocated to arm 3 or 4 with the new concizumab PPX dosing regimen.

For both analysis sets, the specific treatment arms refer to the treatment arms the patients enter after restart.

10.3 Statistical analyses

The statistical analysis plan (SAP) was updated prior to the first patient restarting the trial to reflect the changes made in protocol amendment #4, and includes a more technical and detailed elaboration of the statistical analyses.

As described in Section 5, several evaluations will be made prior to the end of this trial. This section will describe the analyses of the primary and the secondary confirmatory endpoints at the confirmatory analyses cut-off focusing on the randomised arms as well the within-subject comparison in arm 4 of the confirmatory secondary endpoints.

The bleed rate is defined as the number of treated bleeds over the respective observation periods. As a general rule, a treated bleed is defined as any bleed where a factor-containing product is reported between the start and stop time of a bleed. Multiple bleeding locations occurring at the same time point will be counted as one bleeding episode. Further, the endpoints will not include re-bleed. A re-bleed is defined as a bleeding episode (worsening of bleeding site conditions e.g. swelling, pain) starting within 72 hours after stopping treatment of a previous treated bleeding episode (or re-bleed) at the same anatomical location. Note that there can be more than one re-bleed related to the same bleed. If a bleeding episode occurs in the same location more than 72 hours after stopping treatment of a previous bleeding episode or re-bleed in the same location, the bleed is defined as a new bleeding episode.

The Type-I error for testing the two confirmatory hypotheses related to bleeds will be preserved by using hierarchical testing. The tests will be evaluated separately for the two patient populations, i) patients with haemophilia A and ii) patients with haemophilia B. The conclusion from the trial will be drawn for each of the two populations separately, i.e. the conclusion from one population does not influence the conclusion from the other population. Correction for multiplicity between the two populations is therefore not considered relevant. The type 1 error will be controlled for the two hypothesis within one population, as described below.

The overall significance level is 5%. If a hypothesis is confirmed, the significance level will be reallocated to the next hypothesis in the hierarchy and then that hypothesis will be tested at the 5% significance level. This process will be repeated until no further hypotheses can be confirmed.

The primary endpoint is analysed using negative binomial regression. Superiority of concizumab prophylaxis over no prophylaxis in the patient population will be concluded if the two-sided 95% confidence interval of the treatment ratio is below 1.

If superiority is concluded for the primary endpoint the confirmatory secondary hypothesis will be tested with a significant level of 5%. The confirmatory secondary hypothesis aims at comparing the

Page:

89 of 138

bleeding rate during concizumab treatment with the bleeding rate on the patients' previous prophylaxis.

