- Treatment regimens: a) intravenous PPX treatment with factor-containing products and b) PPX treatment regimen with subcutaneous concizumab consisting of an initial loading dose of 1.0 mg/kg, followed by an initial daily dose of 0.20 mg/kg (during the dose adjustment period) and followed by a maintenance dose of either 0.15, 0.20 or 0.25 mg/kg. During both treatment regimens, breakthrough bleeds can be treated intravenously with factor-containing products.
- **Population-level summary**: The treatment ratio of the ABRs between the two treatment regimens.

- **Intercurrent events**: 1) permanent treatment discontinuation in trial 4307, 2) temporary treatment discontinuation, 3) use of factor products not related to treatment of a bleed in trial 4307, 4) minor surgery, and 5) major surgery (during the non-interventional study 4322).
- **Target patient population**: HA patients on stable PPX treatment for at least 24 weeks in the non-interventional study 4322 and have started the concizumab maintenance dose PPX regimen (i.e., completed the dose adjustment period).

The same five components apply for the estimand for HB patients where HA in the target patient population is substituted with HB.

Utilizing these five components, the estimand for the secondary efficacy objectives can be described as the treatment ratio of the ABRs for treated spontaneous or traumatic bleeding episodes:

- For the previous PPX treatment (study 4322): From the point in time where PPX treatment is stable and up until the end of the study.
- For concizumab PPX (trial 4307): from the point in time where the maintenance dose is confirmed, escalated or de-escalated and up until the confirmatory analyses cut-off.

between the two PPX treatment regimens in the target patient population while patients are adhering to the allocated treatment regimens.

The strategies for how to account for the intercurrent events in the estimand are as follows:

- 1. Permanent treatment discontinuation. This intercurrent event is only applicable when a patient is part of trial 4307 (after the dose adjustment period) because if permanent PPX treatment discontinuation occurs for a patient in the non-interventional study 4322 then this patient is not part of the target patient population. If the intercurrent event occurs in trial 4307 then the data from the period after permanent discontinuation of trial treatment are not included and there will be no imputation of missing data.

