- 2. Temporary treatment discontinuation. For this intercurrent event the 'treatment policy' strategy is used meaning that the data from this period are included.
- 3. Use of factor products not related to treatment of a bleed in trial 4307. For this intercurrent event, the data during this period are not included and there will be no imputation of missing data.
- 4. Minor surgery. For this intercurrent event the 'treatment policy' strategy is used. The definition of minor surgery is outlined in Table 14.
- 5. Major surgery: This intercurrent event is only applicable when a patient is part of the non-interventional study 4322 because planned major surgery is not allowed in trial 4307 after restart. Thus, for a fair comparison this intercurrent event will be handled by use of the 'hypothetical strategy' meaning that the data, from the start of the major surgery and until the stop date when post-surgical period has ended and the patient resumes the regular treatment regimen, will be excluded. The definition of major surgery is outlined Table 14.

25 March 2021 Novo Nordisk Date: Version: 5.0 Status:

Page:

Final 34 of 138

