5.2.1 Concizumab prophylaxis

When patients are randomised/allocated to concizumab prophylaxis, they will receive a loading dose of 1.0 mg/kg concizumab at visit 2a (arm 2, 3 and 4) or visit 9a (arm 1) followed by an initial daily dose of 0.20 mg/kg concizumab from treatment day 2. Within an initial 5–8-week dose adjustment period on 0.20 mg/kg concizumab, the patients can be increased or decreased in dose to 0.25 mg/kg or 0.15 mg/kg concizumab. A potential dose adjustment will take place at visit 4a.1 or

Page:

44 of 138

9a.3 and will be based on the concizumab exposure level measured at the previous visit 4a or 9a.2. Patients who have concizumab exposure levels of 200–4000 ng/mL will stay at 0.20 mg/kg concizumab. The new concizumab dosing regimen is shown schematically in Figure 2 and explained in further detail in Section 9.2.2.

Abbreviation: LD = loading dose

Notes: Concizumab exposure level is measured at V4a/9a.2; Potential dose adjustment will take place at V4a.1/9a.3.

Figure 2 Concizumab dosing regimen upon re-initiation of trial

Doses, including the loading dose, given at PK/PD visits (i.e. visit 2a and 9a) will be administered at the site; all other injections may be administered at home by the patient or caregiver.

Prior to visit 2a, patients must be in a non-bleeding state 48 hour prior to the visit however patients can have treatment for up to 24 hours prior to visit 2a, except for treatment with aPCC and ByClot® where the wash-out is 48 hours prior to visit 2a. For patients coming from a PPX treatment regimen, an interval of 2 half-lives from the given factor product to first concizumab dose is required.

A pre-filled, multi-dose pen-injector for the drug administration will be provided by Novo Nordisk, details can be found in Section 7.1.1.

Use of factor-containing products not associated to a bleed is not allowed, except for diagnostic procedures, intramuscular injections (e.g. vaccinations) and minor surgery, e.g. dental treatment, endoscopies etc.

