10.3.2 Secondary endpoints

10.3.2.1 Confirmatory secondary endpoints

The confirmatory secondary endpoint for haemophilia A patients is defined in Section 4.3.2.1.

Only the subset of patients from the FAS that entered the maintenance period in arm 4 and who were on a stable PPX regimen for at least 24 weeks in NN7415-4322 (explorer 6) will contribute to the analysis. The analysis will be done using a negative binomial regression, where the patients' number of bleeds will be analysed with exposure time as offset, treatment and bleeding frequency (<9, ≥9 bleeding episodes during the past 24 weeks prior to screening) as factors and within-subject repeated measurements will be incorporated using of an unstructured covariance structure. The estimated ratio of ABR between the treatment regimens (concizumab prophylaxis versus previous prophylaxis) with corresponding 95% confidence interval and also estimates of the actual ABRs with corresponding 95% confidence intervals in each treatment period will be presented. Non-inferiority will be confirmed if the upper limit of 95% confidence interval is below 2.0.

A similar approach will be used for haemophilia B patients.

Sensitivity analyses

The below sensitivity analyses will be implemented by haemophilia type to further investigate the underlying assumptions of the above statistical analyses. Note that as different strategies are implemented to address some of the intercurrent events, this analysis addresses a slightly different estimand:

- In order to investigate the missing at random (MAR) assumption, a tipping point analysis will be implemented where patients that permanently discontinue concizumab treatment after the dose is decreased, increased or confirmed and before 24 weeks of treatment have been observed will be modelled with an increasing bleeding rate until the conclusion of non-inferiority is changed. For those patients that permanently discontinues treatment before 24 weeks on maintenance dose, the offset period will be fixed at 24 weeks. For any patient that permanently discontinues treatment before the confirmatory analyses cut-off but after 24 weeks on maintenance dose will not be considered to have missing data for the purpose of this tipping point analysis.

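### As written, the treated-bleed rule does not exclude scheduled prophylactic infusions in study 4322, so it could raise the comparator bleeding rate in the within-patient non-inferiority test

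*Protocol*

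**What the plan says.** Section 10.3 of the protocol covers both the primary analysis and the arm 4 within-patient comparison. It states, as a general rule, that "a treated bleed is defined as any bleed where a factor-containing product is reported between the start and stop time of a bleed". Purpose is not mentioned. The week-56 SAP repeats the rule in Section 5.1.

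The within-patient comparison (Section 10.3.2.1) uses arm 4 patients "who were on a stable PPX regimen for at least 24 weeks in NN7415-4322 (explorer 6) will contribute to the analysis". Their comparator regimen in Section 4.2 is "intravenous PPX treatment with factor-containing products". On concizumab, Section 5.2.1 says: "Use of factor-containing products not associated to a bleed is not allowed", apart from diagnostic procedures, intramuscular injections and minor surgery.

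The secondary estimand in Section 4.2 lists as an intercurrent event "use of factor products not related to treatment of a bleed in trial 4307", and its strategy is: "For this intercurrent event, the data during this period are not included and there will be no imputation of missing data". There is no counterpart for study 4322. The two sensitivity analyses in Section 10.3.2.1 are a tipping-point analysis for discontinuation and an all-treatment-policy analysis. Neither varies how a bleed is classed as treated.

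**The concern.** The same sentence can define two different endpoints in the two periods being compared. On concizumab, a minor bleed that the patient leaves alone has little chance of coinciding with a factor dose, so it stays untreated and uncounted. In 4322, a similar bleed could coincide with a routine infusion and be counted.

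Extra counted bleeds in 4322 raise the denominator of the concizumab/previous-prophylaxis ratio and make it easier for the upper confidence limit to fall below 2.0. At stake are the two confirmatory non-inferiority claims (HA and HB), each planned on 30 patients. Elsewhere Section 4.2 does correct for a difference between the two studies: it removes periods of major surgery in 4322 so that the comparison is fair. No such step is stated for scheduled infusions.

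**Working it through.** **Inputs from the protocol (Sections 10.1, 10.3.2.1 and 5.5.1).** n = 30 per haemophilia type; 38 weeks on previous prophylaxis and 24 weeks on concizumab; previous-prophylaxis ABR 4; concizumab ABR 5 (least favourable planned value); yearly over-dispersion 13; frailty correlation 1 (0.8 as the alternative); margin 2.0; historical on-demand/prophylaxis ratio with lower 95% limit 5.90.

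**Step 1: reproduce the plan's power.** Counts are Poisson with mean ABR × T × f. The frailty f is gamma with mean 1 and shape ABR/12, so that yearly variance/mean is 13. T is 38/52.18 or 24/52.18 years. The log ratio is b = ln(m2/T2) − ln(m1/T1), where m1 and m2 are the mean counts. Its robust variance is Σ(y2/m2 − y1/m1)²/n². Non-inferiority is declared if b + 1.96·SE < ln 2. Simulated power at ABR 5 versus 4 is 79%, against the stated figure of at least 79%. Other Table 17 cells agree: 62.5% against 61% (5 vs 4, margin 1.8), 17% against 17% (7 vs 4, margin 2.0), and at correlation 0.8, 48% against 46% (5 vs 4, margin 2.0).

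**Step 2: add relabelling.** Let x be untreated 4322 bleeds counted as treated, divided by truly treated ones. *This is an assumption; the documents give no value.* The comparator ABR becomes 4(1+x) and the observed ratio becomes the true ratio/(1+x). Passing at 2.0 therefore means passing at a true margin of 2(1+x). The preserved share of the historical effect on the log scale is 1 − ln(2(1+x))/ln(5.90).

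| x | Comparator ABR | Effective margin | Effect preserved | False non-inferiority at true ratio 2.0 (correlation 1) |
|---|---|---|---|---|
| 0 | 4.0 | 2.0 | 61% | 4% |
| 0.05 | 4.2 | 2.1 | 58% | 7% |
| 0.10 | 4.4 | 2.2 | 56% | 12% |
| 0.14 | 4.56 | 2.28 | 54% | 16% |
| 0.21 | 4.84 | 2.42 | 50% | 26% |

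At correlation 0.8 the rise is smaller: 3.9% at x=0, 8% at 0.10 and 15% at 0.20. The 4% at x=0 already exceeds the nominal one-sided 2.5% without any relabelling, so the increase is what matters here, not the level.

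**Step 3: what x might be.** Take x = u × min(1, D/I), with u the ratio of untreated to treated bleeds, D the bleed duration and I the infusion interval. All three are assumptions.

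- u = 0.1, D = 0.5 day, I = 3.5 days: x = 0.1 × 0.143 = 0.014
- u = 0.25, D = 1, I = 7 (weekly): x = 0.25 × 0.143 = 0.036
- u = 0.25, D = 1, I = 3.5: x = 0.25 × 0.286 = 0.071
- u = 0.5, D = 1, I = 3.5 (twice weekly): x = 0.5 × 0.286 = 0.143
- u = 0.5, D = 1, I = 7/3 (three times weekly): x = 0.5 × 0.429 = 0.214
- u = 0.5, D = 2, I = 2: x = 0.5 × 1 = 0.50

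So x runs from about 0.01 (effective margin 2.02, negligible) to 0.50 (effective margin 3.0, false non-inferiority 68%).

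**The case against.** The strongest reply is that the rule is expressly a general one and that the governing details lie elsewhere. The confirmatory SAP version 5 and the 4322 protocol and data structure are not among the documents. An exception in either would settle the matter. In 4307, bleed treatment is entered with the bleed (Section 9.2.3), so factor reported for a bleed may simply mean factor entered as its treatment. This stands as a limit on certainty. It does not settle the reading, because Section 7.6 collects haemostatic medication whether or not it relates to a bleed. Two programmers could derive different endpoints from the same sentence.

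A reader might infer that the error can only run one way. The documents do not support that:

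- A relabelled bleed becomes a previous treated bleed, so a later bleed at the same site within 72 hours of stopping treatment would drop out as a re-bleed. This offsets part of the effect, and the simulation does not model it.
- A patient with an infusion due may use it as the treatment. Counting that bleed is correct, and a strict purpose-only rule could miss it.
- The permitted exceptions in Section 5.2.1 leave a small chance of the same overlap on concizumab.

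The main direction is still towards a higher comparator ABR, because scheduled factor is present in only one of the two periods.

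**Conclusion.** The point holds as a defect in the rule as worded: followed literally in 4322, it would mainly raise the previous-prophylaxis ABR and ease passing the margin. No planned sensitivity analysis would show it. The effect is confined to the confirmatory secondary within-patient comparison. The randomised comparison of arms 1 and 2 is untouched, since neither arm has scheduled factor prophylaxis, and the stated 79% power is not in question.

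A reader might go further and conclude that the comparator rate is in fact inflated, or that the non-inferiority claims are unsound. The documents do not support that, because they do not show how 4322 infusions were recorded, how the confirmatory derivation handled them, or what x is. The error rates above are conditional on x and on the model that reproduces the plan's power. They show that relabelling 5% to 10% would already matter (7% to 12% false non-inferiority against 4%), and that a percent or so would not.

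**What to change.** In Section 10.3 and the confirmatory SAP, unless version 5 already does so:

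1. Count a bleed as treated only if factor is recorded as given to treat that bleed, including a prophylactic dose recorded as used or brought forward for it. Apply this in both periods and to the 72-hour re-bleed clock.
2. Where 4322 data cannot separate the two uses, flag those bleeds and repeat the non-inferiority analysis with them counted as untreated.
3. Add a within-patient sensitivity analysis on all bleeds, treated and untreated.

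The week-56 SAP (Section 5.5.1) treats the within-patient comparison as already concluded. If so, state which rule the derivation used and report how many 4322 bleeds change class under item 1.

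The cost is a wording change, a derivation flag and two extra runs of an existing model. The previous-prophylaxis ABR may fall somewhat, making non-inferiority slightly harder to show. A purpose-only rule could also undercount comparator bleeds that a patient managed with an infusion already due; the all-bleeds analysis addresses that.
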